### **8.2.2.4. Serology Testing**

Baseline and Day 22 blood samples will be tested for quantitative anti-SARS-CoV-2 antibodies.

## **8.2.3. Pharmacokinetics Assessments**

Blood samples for pharmacokinetics analysis will be sent to the central laboratory by the site and shipped to a referral laboratory for analysis. Sample collection and handling details will be included in the central laboratory manual.

## **8.2.4. Plan for Monitoring Viral Resistance**

If any Day 10 nasopharyngeal swab sample is positive for SARS-CoV-2 by the SARS-CoV-2 assay or for EV/RV by the ePlex RPP, the Baseline and Day 10 nasopharyngeal swab samples for the subject will be tested for post-treatment reduced susceptibility to tizoxanide.

## **8.3. Subject Diary**

The subject diary will be used to generate primary efficacy data. Therefore, diary compliance is of critical importance.

### **8.3.1. Subject Diary Completion**

Subjects will complete a diary including:

- Oral temperature taken using the study thermometer twice daily (morning and evening), and

- The FLU-PRO© symptoms questionnaire daily in the evening.

The diary will be completed using the subject's smartphone or provisioned device.

Site staff will ensure subject access and ability to complete the diary during the Baseline visit. Subjects will complete the first post-Screening diary at home on the evening of study Day 1.

Subjects will receive electronic reminders to complete the diary daily to ensure compliance.

### **8.3.2. Subject Diary Compliance Monitoring**

It is the responsibility of the clinical site to ensure that subjects are completing the diary as directed. E-mail notifications will be sent to the site daily with a list of subjects who missed the previous day's diary in order to direct follow-up contact with the subject to re-train on the importance of the diary. Site staff may also view a diary completion report at any time within the EDC system.

## **8.4. Adverse Events and Serious Adverse Events**

### **8.4.1. Definitions**

The following definitions will apply to the reporting of adverse events:

1. **Adverse Event:** Any unwanted physical, psychological or behavioral change experienced by a subject during the course of the study and after taking the first dose of study medication regardless of its severity or relation to the study. Adverse events may include symptoms, signs, unexpected worsening of pre-existing conditions, clinically significant changes in laboratory values, diseases and syndromes, and significant and unexpected failures of pharmacological action of other medications. Symptoms of viral respiratory infections (VRIs) (cough, sore, throat, nasal obstruction, fatigue, headache, myalgia, or feverishness) will not be reported as adverse events.
2. **Serious Adverse Event:** Any adverse experience occurring at any dose that is fatal or life threatening; requires in-patient hospitalization or prolongation of an existing hospitalization; is a persistent significant disability/incapacity; is a congenital anomaly or birth defect; or is an important medical event that may not result in death, be life-threatening, or require hospitalization but, based upon appropriate medical judgment, may jeopardize the subject and may require medical or surgical intervention to prevent one of the outcomes listed above.
3. **Unexpected Adverse Event:** Any adverse experience that is not identified in nature, severity, or frequency in the Investigator's Brochure for NTZ.
4. **Severity of adverse events** will be assessed as mild, moderate, severe or potentially life-threatening by the Investigator using the Toxicity Grading Scale Tables provided in [Appendix 4](#) (derived and adapted from "Guidance for Industry: Toxicity Grading Scale for Healthy Adult and Adolescent Volunteers Enrolled in Preventive Vaccine Clinical Trials", US Dept. of HHS, FDA, CDER, September 2007 and the National Institutes of Health, National Cancer Institute Common Terminology Criteria for Adverse Events (CTCAE) version 5.0).
5. **Causality (relationship to treatment)** will be assessed as follows:

- *Definitely Related*: The adverse event is clearly related to the investigational agent(s) or research intervention: the adverse event has a temporal relationship to the administration of the investigational agent(s) or research intervention, follows a known pattern of response, and no alternative cause is present.
- *Probably Related*: The adverse event is likely related to the investigational agent(s) or intervention: the adverse event has a temporal relationship to the administration of the investigational agent(s) or research intervention, follows a known or suspected pattern of response, but an alternative cause may be present.
- *Possibly Related*: There is a reasonable possibility that the event may have been caused by or is linked in a significant way to the research; the adverse event has a temporal relationship to the administration of the investigational agent(s) or research intervention, follows a suspected pattern of response, but an alternative cause is present.
- *Unrelated (or Not Related)*: The adverse event is clearly NOT related to the investigational agent(s) or intervention: the adverse event has no temporal relationship to the administration of the investigational agent(s) or research intervention, follows no known or suspected pattern of response, and an alternative cause is present.

Under double-blind treatment conditions, it should be assumed that all subjects are taking the test drug.

#### **8.4.2. Recording and Follow Up of Adverse Events**

At the time of each visit, the subject will be questioned regarding the occurrence and nature of any adverse events and all events will be recorded in the subject's medical records and in the EDC system. Any subject affected will be examined by the Investigator as deemed necessary to ascertain the course of the event and any residual effects. All adverse events must be followed until their resolution or stabilization even beyond the planned study period.

All moderate and severe adverse events will be reviewed by the Principal Investigator who will determine using his/her best clinical judgment whether they warrant the subject to be discontinued from the study. The Sponsor will be notified immediately if a subject is discontinued from the study. For all adverse events that require the subject to be discontinued from the study, relevant clinical assessments and laboratory tests will be repeated as clinically indicated until final resolution or stabilization of the event(s).

All subjects will be instructed to contact the Investigator, Investigator's assistants, or clinical personnel should the subject have any serious adverse experiences.

An overdose is defined as any intentional or unintentional consumption of the drug by any route that exceeds the highest dose stated in the Investigator's Brochure or in an investigational protocol, whichever dose is larger. Overdoses without an associated adverse event should be recorded, but not reported as an adverse event.

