## 1.2. Schedule of Assessments

**Table 1: Schedule of Assessments**

Assessment	Screening	Baseline	Treatment Period	Diary Period	Follow-Up Visits				Unscheduled
	Day 1	Day 1	Day 2-7	Day 1-21	Day 4±1	Day 10±3	Day 22±3	Day 28±3	As Needed
Signed informed consent/assent 	X								
Demographics, smoking & medical history 	X								
Urine pregnancy test 	X								
Physical examination 	X				X 	X 	X 		X 
Body weight and resting vital signs 	X				X	X	X		X
Complete Screening FLU-PRO 	X								
Evaluate eligibility 	X								
Collect nasopharyngeal swabs 		X			X	X			
Collect blood sample for lab safety tests 		X					X		X
Collect blood sample for antibody tests 		X					X		
Collect blood sample for pharmacokinetics 					X				
Collect urine sample for routine urinalysis 		X					X		X
Record concomitant medications		X			X	X	X		X
Randomize & dispense study medication 		X							
First dose and practice diary in-office 		X							
Review/record adverse events 		X			X	X	X		X
Instructions re: dosing, concomitant medications, diary completion, follow-up visits, and emergency care 		X	X		X	X	X		X
Contact subject to screen for complications			X 					X 	
Complete diary (subject responsibility) 				X					
Review subject diary entries (site responsibility) 				X					

 See [Section 8.1.1](#)

 See [Section 8.1.2](#)

 See [Section 8.1.3](#)

 Completed as necessary, see [Section 8.1.3](#)

 See [Section 8.1.4](#)

 See [Section 8.1.5](#)

 See [Section 5.0](#)

 See [Section 8.2](#)

 See [Section 8.1.6](#)

 See [Section 8.3.1](#)

 See [Section 8.4](#)

 See [Section 8.1.7](#)

 See [Section 8.1.8](#)

 See [Section 8.1.9](#)

 See [Section 8.3.2](#)

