## 6.4. Study Intervention Compliance

Subject compliance with study medication will be checked by site staff daily during the treatment period. Subjects will return the treatment kit with any unused medication to the clinic at the Day 10 visit. Subjects will be considered non-compliant (major protocol deviation) if they have missed more than two doses of the study medication during the first three days of the study. Non-compliance will not be cause for discontinuation of subject participation in the study.

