## 7. STUDY INTERVENTION DISCONTINUATION AND PARTICIPANT DISCONTINUATION

Treatment will be discontinued for individual subjects for the following reasons:

1. An allergic reaction occurs or is suspected.

2. Medical conditions that may require study medication discontinuation in the Investigator's judgment.
3. Subject desire to discontinue participation.

In the case of an allergic reaction or other medical condition requiring subject discontinuation, appropriate treatment will be instituted by the Investigator.

Subjects will be encouraged to complete all protocol-specified follow-up visits even if study drug is withdrawn.

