#### 9.4.1. Efficacy Analyses

Efficacy analyses will be based on a population consisting of all subjects randomized who receive at least one dose of study medication and are positive for SARS-CoV-2 by Aptima® SARS-CoV-2 Assay at Baseline. For time-to-event analyses, a test of significance (as described in the following) will be performed with descriptive statistics provided, including the use of Kaplan-Meier figures.

There will be one primary efficacy analysis:

- Time to Sustained Response for the NTZ treatment group will be compared to that of the placebo treatment group using a stratified Gehan-Wilcoxon test ( $\alpha=0.05$ ) where stratification will follow that used for randomization. Subjects without a Sustained Response recorded will be treated as censored as of the last diary without a documented Sustained Response, except for subjects who are hospitalized or die during the study, who will be censored at Day 21 (hour 504).

Sensitivity analyses for the primary efficacy analysis will be described in the Statistical Analysis Plan.

If the primary analysis is significant at the 0.05 level, the key secondary efficacy analysis will be formally evaluated at the 0.05 level as follows:

- Proportions of subjects progressing to Severe COVID-19 Illness will be compared between the treatment groups using a Cochran-Mantel-Haenszel (CMH) test stratified by the randomization strata.

Exploratory analyses will be performed as follows:

- Proportions of subjects positive for SARS-CoV-2 by Aptima® SARS-CoV-2 Assay at study Day 4 and Day 10 will be compared between the treatment groups using a Cochran-Mantel-Haenszel (CMH) test stratified by the randomization strata.
- Mean changes from baseline in quantitative SARS-CoV-2 RNA measured by RT-PCR at Day 4 and Day 10 will be compared using a t-test.
- Proportions of subjects hospitalized due to COVID-19 or complications thereof will be compared across the treatment groups using a CMH test stratified by the randomization strata.
- Proportions of subjects with mortality related to COVID-19 or complications thereof will be compared across the treatment groups using a CMH test stratified by the randomization strata.

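### Section 8.4.2 allows removal from the study, not only from study drug, for an adverse event; keeping these subjects in the existing follow-up is a cheap improvement with a small expected effect

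*Protocol*

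**What the plan says.** Protocol Section 8.4.2 asks the Principal Investigator to review all moderate and severe adverse events and "determine using his/her best clinical judgment whether they warrant the subject to be discontinued from the study". It adds that "The Sponsor will be notified immediately if a subject is discontinued from the study". For these subjects it then calls for assessments and laboratory work relevant to the event, until the event resolves or stabilises. It says nothing about the diary, the scheduled visits or the Day 28 contact.

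Section 7 deals with stopping treatment and says "Subjects will be encouraged to complete all protocol-specified follow-up visits even if study drug is withdrawn". Table 1 places Day 28 among the follow-up visits, and the row "Contact subject to screen for complications" is marked there, so that contact is already encouraged after drug withdrawal. The diary is not named in Section 7, although Section 8.3 states "The subject diary will be used to generate primary efficacy data".

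For missed doses the protocol does separate drug-taking from participation (Section 6.4): "Non-compliance will not be cause for discontinuation of subject participation in the study". It makes no matching statement for adverse events.

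On the analysis side, Protocol Section 9.4.1 provides "Subjects without a Sustained Response recorded will be treated as censored as of the last diary without a documented Sustained Response", with exceptions for death and hospitalisation (in SAP Section 4.1.1, hospitalisation due to COVID-19). SAP Section 4.2.1.3 moves subjects who discontinue the study to hour 504, but only as a sensitivity analysis.

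**The concern.** Dosing lasts 5 days, the diary 21 and the study 28. After Day 5 there is no drug left to stop, so removing a subject from the study for an adverse event ends only the observation.

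Two endpoints are exposed:

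- **Primary.** A removed non-responder who has not died or been hospitalised is censored at the last diary, because of a decision that may be related to the course of illness. A subject who leaves after one relapse-free diary counts as a responder, with any later relapse unseen (SAP Section 4.1.1).
- **Key secondary.** Progression to severe illness has no rule for a missing outcome. SAP Section 2.3 covers dates only, Section 4.2.1.3 covers the primary endpoint only, and Section 4.2.2.1 gives none. Progression after removal may be captured less reliably.

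The loss is avoidable because the diary, reminders, visits and calls are already in place.

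**Working it through.** **1. The plan's own figure.** Protocol Section 9.1 takes 312 subjects (90% power, two-sided alpha 0.05, enterovirus/rhinovirus curves), allows about 10% for early discontinuation or missing data, and arrives at 350 or more. 312/(1 − 0.10) = 347 and 312 × 1.10 = 344 (rounded up), so the step reproduces to within 2%. The 312 itself cannot be rebuilt without the Kaplan-Meier curves.

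**2. How many subjects.** Protocol Section 2.2.3 reports under 1% stopping therapy for adverse events in earlier trials. That concerns therapy, not study exit, so it is a proxy and not a bound. 0.01 × 350 = 3.5; 0.01 × 400 = 4.

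**3. Power.** Set the noncentrality at 1.960 + 1.282 = 3.242 for n = 312, so power = Φ(3.242 × √(n/312) − 1.960). Assume the 10% allowance is used up, and count a lost subject as contributing nothing.

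- N = 350: n = 315 gives 90.3%; keeping 3.5 more (n = 318.5) gives 90.6%, a gain of 0.3 points.
- N = 400: n = 360 gives 93.6%; n = 364 gives 93.8%, a gain of 0.2 points.
- At assumed removal rates of 0.5%, 2% and 3% with N = 350, the gain is 0.15, 0.6 and 0.9 points.

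**4. Type I error.** Simulation of the stratified Gehan-Wilcoxon test: 175 per arm, 8 near-equal strata, daily diary, cut-off at Day 21, no treatment effect, 20,000 runs per case. Response times are assumed lognormal with median 201.8 h (placebo coronavirus subjects, Protocol Section 2.2.4). Sigma is 0.81, since ln(201.8/117)/0.6745 = 0.81 matches the lower quartile. The alternative is 1.40, since an upper quartile above 504 h needs more than ln(504/201.8)/0.6745 = 1.36. Four removed subjects are censored on Days 1 to 5. Slow means the slowest quarter. Each case reuses the same simulated trials, so the changes in z are paired; positive favours NTZ.

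| Case | Two-sided rejection, sigma 0.81 / 1.40 | Mean change in z |
|---|---|---|
| No removals | 5.03% / 5.00% | – |
| 4 random non-responders, both arms | 5.04% / 4.95% | – |
| 4 slow responders, both arms | 5.11% / 5.17% | 0.000 / 0.000 |
| 4 random non-responders, all NTZ | 5.14% / 5.19% | +0.053 / +0.051 |
| 4 slow responders, all NTZ | 5.78% / 5.66% | +0.236 / +0.193 |
| Same 4, set to hour 504 | 4.78% / 4.93% | −0.045 / −0.004 |

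The standard error of a rejection rate near 5% is √(0.05 × 0.95/20,000) = 0.15 points. In the slow, all-NTZ case, significant results favouring NTZ rise from 2.51% / 2.57% to 4.31% / 4.11%.

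**5. Key secondary.** The documents give no progression rate. If each of 4 removed subjects had a 2% to 10% chance of later progression (assumption) and nothing else captured it, 4 × 0.02 = 0.08 to 4 × 0.10 = 0.4 events would be missed. The total would be 350 × 0.02 = 7 to 400 × 0.10 = 40. At 25% each, 4 × 0.25 = 1 event would be missed.

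**The case against.** The strongest reply is that this is only loose wording. Section 8.4.2 adds a duty to follow the event and does not say that the diary or visits stop. Section 7 covers both treatment and participant discontinuation and uses the two ideas almost interchangeably, so its encouragement could be read as covering removed subjects too. Staff must remind subjects about the diary at each contact (Section 8.1.7), and the missed-diary notices in Section 8.3.2 do not depend on dosing.

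Other routes also limit the loss. The Day 2-7 calls ask about breathlessness at rest, and hospital oxygen records are sought on referral (Section 8.1.8). Adverse events are followed to resolution or stabilisation, and hospitalised subjects are followed up where feasible (Section 8.4.4). The listed symptoms of viral respiratory infection are not reported as adverse events (Section 8.4.1), so the rule will apply rarely. Version 4.0 took effect on January 11, 2021, in the last planned month, so few subjects could benefit.

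Much of this stands and is why the point is minor. It does not close the gap: no passage says that a subject removed from the study continues the diary or the scheduled contacts. The objection that the missing-outcome rule for the key secondary endpoint is a wider question is also fair, because that affects every dropout. Retaining these subjects reduces the need for such a rule but does not supply one.

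**Conclusion.** The concern holds as a minor design point. The rule as written allows avoidable last-diary censoring and less reliable capture of later progression, on a case-by-case decision by the Investigator.

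The expected effect is small: about 4 infected subjects, 0.2 to 0.3 points of power, and a type I error indistinguishable from 5% unless all the losses are slow responders in one arm. That last case is contrived, and the planned hour-504 sensitivity analysis removes the shift in z.

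No direction of bias is shown: Section 2.2.3 reports adverse event rates similar to placebo apart from chromaturia. The primary result is not shown to be at risk.

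These sizes rest on the therapy-discontinuation proxy, the assumed lognormal response times and the assumed progression rates.

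**What to change.** In Section 8.4.2, state that an adverse event may warrant stopping study medication but is not in itself a reason to end participation. Keep immediate sponsor notification for stopping either one.

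In Section 7, state that the diary to Day 21 and the visits and contacts to Day 28 continue after study drug is stopped, or after an adverse event that occurs once the 5-day course is complete. The exceptions are withdrawal of consent and an Investigator's judgment that continued assessments would be unsafe. When to stop the drug remains the Investigator's clinical decision.

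The cost is a short amendment, with IRB approval unless it counts as purely administrative (Section 10.1.1), plus continued diary entries and contacts for a few subjects and sites. No procedure is added and the sample size does not change. The edit prevents only investigator-driven losses; subjects can still withdraw or stop the diary. So late in this study, much of its value lies in carrying the wording into later protocols.

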#### **8.4.3. Reporting Requirement**

The Principal Investigator is required to notify The Romark Institute for Medical Research (Sponsor) immediately (within 24 hours of the initial report) of any unexpected, fatal, or life-

threatening experience and all unusual, alarming, or serious reactions to medication regardless of any opinions as to the cause/effect relationship. All serious adverse events will also be reported to the IRB as required by the IRB procedures. Adverse events should be reported to:

The Romark Institute for Medical Research  
Medical Affairs

Tel: [REDACTED] Fax: [REDACTED]

#### **8.4.4. Management of Subjects Requiring Hospitalization**

Subjects requiring hospitalization for any reason during the course of the study will receive local standard of care under the supervision of the hospital's attending physicians. The Investigator will attempt to follow up on the subject to obtain complete data for a narrative of the Serious Adverse Event and complete safety follow up procedures for the study as feasible.

#### **8.4.5. Medication Errors**

[figure not shown]
A medication error is defined as any preventable event related to dosing instructions, product labeling, or packaging that causes or leads to inappropriate medication use or subject harm while the medication is in the control of the investigative site or subject. Medication errors which result in adverse events should be recorded and reported as adverse events. All other medication errors should be reported to the study Sponsor through the Medical Affairs department within 7 days of identification by the site.

### **9. STATISTICAL CONSIDERATIONS**

#### **9.1. Sample Size Determination**

The primary efficacy parameter is the time from first dose to Sustained Response based on the FLU-PRO Patient Reported Outcomes instrument (see [Section 9.3](#)). This response definition was applied to Romark studies RM08-3004 and RM08-3005 in the treatment of influenza and colds caused by *EV/RV*, respectively. Kaplan-Meier curves for the studies are shown below.

**Figure 2: Kaplan-Meier Curves Forming the Basis for Sample Size Calculations**

Based upon the influenza data, a sample size of 288 subjects (144 per group) would provide 90% power to detect a statistically significant difference in the survival distributions between the NTZ and placebo groups (two-sided alpha=0.05). Using the *EV/RV* data yields a sample size of 312 subjects (156 per group). These calculations were performed for the Gehan rank test using SAS PROC POWER (SAS 9.4) with the curves shown above (proportion not responded by the end of each day was used as input) and censoring at day 21. In order to ensure a robust dataset, we have selected a sample size of at least 350 SARS-CoV-2-infected subjects based upon the *EV/RV* data and adding an allowance for approximately 10% of subjects to discontinue early or otherwise have missing data. If the pace of enrollment is high, we will enroll up to 400 SARS-CoV-2-infected subjects.

We anticipate a SARS-CoV-2-positive rate between 50% and 75%. Therefore, we estimate that enrollment of 350-400 SARS-CoV-2 subjects may require enrollment of 450-800 subjects.

